6.4.3 Donor Organ Screening Criteria

All potential donors will be screened at the time an offer is made by an Organ Procurement Organization via telephone. Only the principal investigator ([name]) or a trained, qualified designee will screen potential donors. The medical/social history form must be reviewed for risk of disease transmission. All donors will be screened for safety and for organ quality. All offers will be logged and tracked using a Donor Screening Form and logbook.

Safety screening will include criteria defined in the Suitability Determination for Donors of Human Cellular and Tissue-Based Products Final Rule, as well as current high-risk criteria for bloodborne pathogens defined by the Centers for Disease Control and Prevention. All donors with risk of disease transmission according to these guidelines will be deferred.

All screening criteria are outlined in SOP form. Safety screening exclusion criteria include the following:

- Men who have had sex with another man within the past five years
- Persons who have injected drugs for non-medical reasons within the past five years, including intravenous, intramuscular, or subcutaneous injections
- Persons with hemophilia or related clotting disorders who have received human-derived clotting factor concentrates
- Persons who have had sex for money or drugs within the past five years
- Persons who have had sex with any of the individuals described in the four items above within the past 12 months or with any individual suspected of having HIV or hepatitis B
- Persons who have been exposed within the past 12 months to known or suspected HIV, HBV and/or HCV infected blood through percutaneous inoculation (e.g., needlestick) or through contact with an open wound, non-intact skin, or mucous membrane
- Persons whose history, physical exam, or medical records reveal other evidence of high risk behavior and/or HIV, or hepatitis B or C infection such as: a diagnosis of AIDS and/or hepatitis B or C, unexplained weight loss, night sweats, blue or purple spots on the skin or mucous membranes typical of Kaposi's sarcoma, unexplained lymphadenopathy lasting > 1 month, unexplained > 38.6 degree Celsius temperature for > 10 days, unexplained persistent cough and shortness of breath, opportunistic infections, unexplained persistent diarrhea, male to male sexual contact, sexually

transmitted diseases, needle track marks or other signs of parenteral drug abuse, unexplained jaundice, or hepatomegaly

- Current inmates of correctional systems (including jails and prisons) and individuals who have been incarcerated for more than 72 consecutive hours during the previous 12 months
- Persons who have had close contact with another person having viral hepatitis within the past 12 months (contact which may allow exposure to blood/body fluids including sharing of kitchen/toilet facilities)
- Persons who within 12 months prior to donation have undergone tattooing, acupuncture, or body piercing in which shared instruments are known to have been used
- Persons with history/symptoms of spongiform encephalopathy (CJD) or known family history (blood relative) of a person with non-iatrogenic CJD
- Persons with dementia or degenerative neurologic disorders of viral or unknown etiology
- Persons who have received injections of human pituitary-derived growth hormone (pit-HGH)
- Persons known to have received transplants of human dura matter
- Persons who have had a xenotransplant of any type
- Septicemia

When the offer is made, blood type, consent, and serology results are verified and blood type is recorded. The informed consent for transplant/research is identified. Required serologies (HIV-1 and 2, hepatitis B surface antigen, HCV, HTLV I and II, and syphilis) are performed using FDA approved assays and must be negative/non-reactive (see *Appendix Letter of confirmation by collaborating organ procurement agencies*). A sample that tests positive for CMV may be accepted if the donor was asymptomatic prior to death.

In addition, the blood sample used for serological testing must not be plasma diluted. A sample will be considered plasma diluted if: a) the donor received more than 2000 cc of blood products/colloids during the 48 hours prior to the blood draw, or b) the donor received more than 2000 cc of crystalloids in the hour prior to the blood draw. In such cases, a Plasma Dilution Worksheet must be used to determine if the sample tested was hemodiluted. Only samples proven to be < 100% diluted will be acceptable.

Screening for organ quality will be done to help ensure an adequate amount of functional islets. Quality screening exclusion criteria include the following:

- Donor age < 15 or > 75 years
- Warm ischemia
- Cold ischemia > 12 hours
- Methanol toxicity
- History of diabetes
- BMI < 19

6.5 Test Material and Administration

6.5.1 Islet Dosing and Administration

A minimum amount of islets of about 10,000 IE/kg recipient body weight is required for engraftment and confirmed C-peptide expression based on the Edmonton series. This form of procedure may require multiple transplants in order to reach this desired minimum number of islets, as previous clinical studies were unable to reliably reach insulin independence with a single transplant.

Eligibility for second or third islet infusion

Subjects are eligible for further transplant if by the end of the fourth week after the first islet infusion or by the end of the fourth week after the second islet infusion they do not meet insulin-independence criteria. If a subject does not reach the definition of insulin independence by the end of the third month after the third transplant, the subject may be considered for an exceptional fourth islet infusion. However, the indication for an exceptional fourth transplant needs to be presented to the Data Monitoring Committee and approval obtained.

Eligibility for islet retransplantation and/or fourth islet transplant:

Subjects are eligible for subsequent islet infusions if after a period of insulin independence of at least 30 days, they present with declining islet function requiring reintroduction of exogenous insulin. Subjects may receive this additional islet infusion anytime during the first year after the last islet infusion, or anytime during the 5-year follow-up, as long as no exclusion criteria are present and avoiding any HLAs (human leukocyte antigens) against which the recipient may have developed donor specific antibodies.

No maximum number of delivered islets is specified, except that the number must exceed 10,000 IE/kg following 2 islet transplants, and packed cell volume may not exceed 10 mL per transplant.

Transplant Procedure

Islets will be isolated from human pancreases procured from deceased multi-organ donors as described in Section 7. The islet isolation procedure will be performed in the clean room facilities of the Cell Isolation Laboratory at the University of Illinois at Chicago Hospital (see Section 7.4 *University of Illinois at Chicago Islet Processing Facility*). Isolated human pancreatic islets will be stored for a maximum of 12 hours before transplantation (see Section 7.2 *Product Manufacturing*).

After the islet lot has been released by the PI, [name], or a co-investigator (see Section 7.6 *Product Testing*), and once the surgeon and subject are ready for infusion, the suspension is drawn directly into sterile 60 mL syringes. The 30 mL of transplant media containing the islets will be aspirated into the 60 mL syringe and the flask will be rinsed with 20 mL of transplant media. The 20 mL of transplant media will be aspirated in the 60 mL syringe. One 60 mL syringe will contain a maximum of 1 mL total packed islet cells. Alternatively to syringes, islets can be infused via a 600-mL iv bag-system.

The preparation will be labeled (see Section 7.3 *Product Label*), packed into sterile bags, and brought to the radiology suite via a hand carried insulating container at room temperature.

The radiology suite in which the procedure will be performed has access to emergency equipment, and the in-house anesthesiologist on call will be available to monitor the subject if necessary. Access to the surgical operation room is granted and a surgical team is available. The PI, [name], is a trained general and transplant surgeon with experience in the management of possible complications that could occur after islet transplantation such as bleeding from the puncture site or inability to access the portal vein by interventional radiology. In the absence of [name], a co-investigator will cover the service.

The subject will be admitted to the hospital as soon as an islet preparation is evaluated as potentially transplantable (sufficient islet mass and purity after purification). While release criteria of the islet cells are being evaluated, an eligible subject will be admitted and hospitalized in the Transplant Unit (7W UIC Hospital), and the immediate pre-transplant work-up will be performed as described in Section 6.6.4. The subject will remain in the Transplant Unit until the islet preparation is shown to fulfill the release criteria and is released for transplantation by the PI or a designee and the cross-match test is reported as negative. Then the subject will be brought to the radiology suite for transplantation. In the event that the islet preparation fails release criteria, the subject will be discharged from the hospital.

Access to the portal vein for islet transplantation is achieved by transvenous or percutaneous transhepatic access under fluoroscopic and ultrasound guidance by the Interventional radiologist co-investigator. If a transvenous technique is used, access to the right jugular vein is obtained using a 21 gauge micropuncture needle under ultrasound guidance. A guiding sheath is advanced across the right atrium and into the right hepatic vein under fluoroscopy. Position is confirmed with injection of contrast media (iodinated contrast or if allergic, CO₂ or gadolinium). Close monitoring of the cardiac rhythm by continuous ECG and pulse oxymeter will be performed to allow rapid response to any cardiopulmonary events including cardiac dysrhythmias. Blood pressure and respiratory rate will be monitored intermittently (at least every 5 minutes). A sheath needle (Colapinto™, Cook, Bloomington, IN) is advanced anteromedially through the hepatic parenchyma under fluoroscopic guidance until access to a peripheral portal vein is obtained. The localization of portal vein puncture is confirmed similarly to the

percutaneous technique described below, and the sheath is advanced into the main portal vein.

For the percutaneous approach, a local anesthetic agent (lidocaine) is injected subcutaneously, and a 21 gauge needle is used to puncture a peripheral branch of the right portal vein. Tiny amounts of angiographic contrast media (iodinated contrast or if allergic, CO₂ or gadolinium) are used to confirm satisfactory location of the puncture site in a peripheral portal vein. A thin, flexible guidewire is threaded into the main portal vein and the needle is exchanged for a 4/6 French Accustick™ catheter (Boston Scientific, Natick, MA). This catheter is threaded over the guidewire to position the tip in the main portal vein. Contrast portogram is obtained with minimal contrast. The catheter is then exchanged over a guidewire for a vascular introducer sheath positioning the sheath tip at the main portal vein to allow ease of infusion of islet cells. The portal pressure is monitored by attaching to an in-line pressure monitor via a 3-way stopcock after zeroing the monitor to room air pressure. Elevated absolute intraportal pressures (> 20 mmHg or > 27 cmH₂O) confirmed at the beginning of the procedure will be considered a contraindication for continuing with the transplant infusion.

If access to the portal vein cannot be gained by transvenous or transcutaneous approach, the subject will be brought to the operation theatre. A small laparotomy will be performed under local or general anesthesia, and portal access will be gained through cannulation of a mesenteric vein (24-26). The surgery will be performed by the PI, [name], or a co-investigator.

The islet preparation may consist of fractions of different purity with a total packed cell volume of less than 10 mL. If the total packed cell volume of the islet preparation is greater than 5 mL, the lot will be divided into two sub-lots during the purification process so that the higher purity fractions may be pooled separately from lower purity fractions and labeled accordingly. Each sub-lot will be divided into syringes (or bags) each containing a maximum of 1 mL of total packed islet cells (if syringes are used). If more than one sub-lot of the islet preparation is to be administered (i.e., where sub-lots are identified as having different islet purity), the lot with the higher purity will be administered first. Mixing sub-lots together for simultaneous administration is not permitted.

The islets will be injected slowly (each syringe over a period of at least 5 minutes) by [name] or a co-investigator. During the injection, the syringe is turned constantly to avoid sedimentation of the islets and clumping. If the bag system is used, the islets are infused by gravity.

Portal pressure will be monitored before and after infusion of one syringe load (50 mL volume containing 1 mL of tissue). Any change in portal pressure will be documented, and if the intra-portal pressure rises above 22 mmHg, infusion of subsequent syringes must be held until the pressure falls below 18 mmHg. If the bag system is used, the portal pressure is taken intermittently, and if the intra-portal pressure rises above 22 mmHg, the infusion must be held until the pressure falls below 18 mmHg. The bag

system must be repetitively and gently shaken to keep the islet preparation in suspension and avoid clumping.

Following each infusion, if the portal pressure remains elevated above 22 mmHg for longer than 10 minutes, then no further infusion will be administered through the hepatic vein, and the procedure will be terminated.

The procedure, duration of injection, number of syringes injected and discarded, and portal pressures will be recorded in the case report form. Also, any adverse event occurring during the transplant process will be recorded in the case report form.

After successful completion of the islet infusion, the catheter and syringe or bag system will be rinsed with an additional 20 mL of transplant media, which is infused through the cannula over approximately 2 minutes, and a final portal pressure documented. Under ultrasound or fluoroscopic guidance with very minimal further contrast use, the sheath tip is withdrawn from the main portal vein into the liver parenchyma. Contrast media (iodinated contrast or if allergic, CO₂ or gadolinium) is used to confirm extraportal position of the sheath. While the subject continues to be monitored, Avitene microfibrillar collagen hemostat (BARD, Davol Inc., Warwick, RI) paste mixed with diluted contrast is injected into the sheath to seal the liver parenchymal tract. Under fluoroscopic guidance the sheath is withdrawn while injecting the Avitene paste until the sheath is removed and Avitene paste seals the liver parenchymal tract to the peripheral portal vein. Alternatively, the catheter is withdrawn slowly over 30 minutes or more, allowing formation of an autologous blood clot. The catheter is then removed completely and the subject returns to the Transplant Unit with instructions to lie recumbent for 4 hours. Abdominal ultrasound and Doppler examination of the liver are performed the day after the procedure to exclude procedure related complications such as portal vein thrombosis or intra-abdominal bleeding (see Section 6.6.6 and Appendix *Post-Transplant Orders*).

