6.4.2 Recipient Exclusion Criteria

Subjects will be excluded from the study if one of the following conditions is present:

1. Diagnosis of co-existing cardiac disease, characterized by any one of these conditions:
 - a. Recent myocardial infarction (within past six months), or
 - b. Angiographic evidence of non-correctable coronary artery disease, or
 - c. Evidence of ischemia on functional cardiac exam (with a stress echo test recommended for subjects with a history of ischemic disease).
 - d. Heart failure > New York Heart Association II
2. Active alcohol or substance abuse includes cigarette smoking (must be abstinent for six months). Active alcohol abuse should be considered using the current National Institute on Alcohol Abuse and Alcoholism definitions.
3. Psychiatric disorder making the subject not a suitable candidate for transplantation, e.g., schizophrenia, bipolar disorder, or major depression that is unstable or uncontrolled on current medication. (A psychological or psychiatric consultation is required only if considered necessary by some current indication or history.)
4. History of non-adherence to prescribed regimens
5. Active infection including hepatitis C, hepatitis B, HIV
6. TB (by history or currently infected as evidenced by a positive QuantiFERON® - TB Gold test or under treatment for suspected TB)
7. Any history of malignancies except squamous or basal skin cancer. Any subject found to have squamous or basal cancer is required to have it removed prior to transplant.

8. Known family history of MEN2 or MCT
9. History of stroke within the past 6 months
10. BMI > 27 kg/m²
11. C-peptide response to glucagon stimulation (1 mg iv) (any C-peptide ≥ 0.3 ng/mL)
12. Inability to provide informed consent
13. Age less than 18 or greater than 75 years
14. Creatinine clearance < 80 mL/min/1.73 m² by 24-hour urine collection. If corrected creatinine clearance is < 80 and serum creatinine is < 1.2 mg/dL, then a nuclear renal scan is required to determine glomerular filtration rate.
15. Serum creatinine consistently > 1.5 mg/dL
16. Macroalbuminuria (urinary albumin excretion rate > 300 mg/24h)
17. Baseline Hb < 12 gm/dL in women or < 13 gm/dL in men

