- An intravenous line is inserted on each arm, and 300 mg/kg of glucose (using a 50% glucose solution) is injected as rapidly as the subject tolerates and within less than 3 minutes. Blood samples for glucose, C-peptide, and insulin measurement are drawn at time -10, -1 (before injection), 2, 3, 4, 5, 6, 8, 10, 15, 20, 30, 40 minutes after glucose injection.
- The acute insulin response will be defined as the mean of the 3, 4 and 5 minutes insulin values with the mean of the basal values (-10 and 0 minute) subtracted.

○ GST, glucagon stimulation test

- Glucose, C-peptide, and insulin levels are measured before and six minutes after injecting a bolus of 1 mg of glucagon (Glucagen[®], Novo Nordisk Pharma SA) or the equivalent intravenously.

○ OGGT, oral glucose tolerance test

- Starting at time 0 the subject consumes a drink containing 75 gm of glucose (in 300 mL solution) over a 5-minute period. Blood samples for glucose, C-peptide, and insulin are drawn before and at 30, 60, 90 and 120 minutes after the subject begins the drink.

○ MMTT, mixed meal tolerance test

- A fasting blood sample for serum glucose, insulin, and C-peptide is drawn just before the test. At time 0, the subject is given Ensure High Protein[®] or Boost[®] to drink in the amount of 6 mL per kg body weight to a maximum of 360 mL, which is to be consumed within 5 minutes. Ninety minutes from time 0, another blood sample is drawn for serum glucose, insulin, and C-peptide.

- Detailed lipid panel
 - Total cholesterol, direct LDL cholesterol, HDL cholesterol, triglycerides, apolipoprotein B, apolipoprotein A1, free fatty acids, and lipid fraction ratio
- Lipid panel
 - Cholesterol, HDL, triglycerides, LDL cholesterol
- Inflammatory panel
 - CRP, MCP, MMP9, CAM, VCAM, fibrinogen, PAI-1 (antigen), TPA
- B-type natriuretic protein (BNP)
- ABO/RH (UNOS requires 2 independent blood type tests)
- Panel reactive antibodies (PRA)
- Antibodies: anti-GAD 65, anti-IA2, anti-islet cell, and anti-insulin
- IL2 receptor saturation
- Archive serum

- Chest x-ray
- Abdominal ultrasound and Doppler
- Thyroid ultrasound (at screening and 52 weeks after final transplant)
- Nuclear renal scan if 24-hour urine corrected creatinine clearance is < 80 mL/min/1.73m² and/or serum creatinine is < 1.2 mg/dL on repeated measurement
- Primary care screening referrals:
 - Women:
 - Mammography annually from age 40
 - Pap test according to current American Cancer Association guidelines
 - Men:

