M/C ratio (random)		X	X	X						X					X					X			X
Sputum culture, sensitivity					#																		
Blood culture, sensitivity					#																		
Glucagon stimulation test	X									X						X							X
Mixed meal test		X														X							X
OGTT										X						X							X
IVGTT										X						X							X
ECG	X			X											X								X
Chest x-ray		X																					X
Abdominal ultrasound, Doppler		X				X																	
Cardiology Consult		X																					
CGMS		X																					X
Primary care	X																						X
Thyroid Ultrasound		X																					X

Visit A: screenings for inclusion

Visits 1 and 2 include 3 evaluations per week; Visit 3 includes 2 evaluations per week; Visits 4 to 7 include 2 evaluations per 2 week period (1 visit per week)

Vital signs: blood pressure, heart rate, respirations, temperature

CMP: comprehensive metabolic profile

CBC: complete blood count

BNP: B-type natriuretic peptide

Antibodies: anti-GAD 65, anti-IA2, anti-islet cell, anti-insulin

IL2 receptor saturation at investigator's discretion

PRA: panel reactive antibodies

Only if hospitalized within the past week

* Only if negative at Screening II

CGMS: continuous glucose monitoring system at Screening A², 1 year after first transplant, 1 year after final transplant

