**** Alternative immunosuppressant trough level only if applicable**

5-Year Follow-Up

Subjects who complete the original 52-week post-transplant evaluation period will be asked to continue follow-up evaluations every three months for five years for safety and efficacy monitoring. All subjects can voluntarily withdraw from follow-up at any time.

The following examinations and blood tests will be performed according to the *Schedule of 5-Year Follow-Up* (Section 6.7.1). Additional evaluations may be required for medical conditions presenting during the study period and according to best medical practice. Should the function of the islet graft decline over time and the subject return to insulin therapy, repeat transplant may be considered.

- History and adverse event and toxicity assessments (reviewed at each visit and recorded at any time necessary)
- Physical exam including vital signs (blood pressure, heart rate, respiratory rate, temperature)
- Body mass index (BMI, body weight in kilograms over square of height in centimeters)
- Electrocardiogram (ECG)
- Comprehensive metabolic profile (CMP):
 - Na⁺, K⁺, Cl⁻, Ca⁺⁺, CO₂, creatinine, BUN, glucose, total protein, albumin, total bilirubin, ALP, AST, ALT, amylase
- Complete blood count (CBC):
 - Hemoglobin, hematocrit, red blood cells, white blood cells, differential
- Urine analyses
 - Urinalysis
 - Creatinine, osmolality, microalbumin, total protein
 - Microalbumin-creatinine ratio)
- Drug levels
 - Tacrolimus and sirolimus, and alternative trough levels if applicable to reach target levels as defined in Section 6.5.2
- Cytomegalovirus (CMV) viral load by real time PCR
- Epstein-Barr Virus (EBV) viral load by real time PCR
- HbA1c, basal C-peptide, fructosamine
- Blood sugar self-monitoring (BS-SM)
- Metabolic tests to evaluate insulin-secretory capacity of the islet graft:
 - IVGTT – intravenous glucose tolerance test
 - GST - glucagon stimulation test
 - OGTT – oral glucose tolerance test
 - MMTT - mixed meal tolerance test
- Detailed lipid panel:
 - Total cholesterol, direct LDL cholesterol, HDL cholesterol, triglycerides, apolipoprotein B, apolipoprotein A1, free fatty acids, and lipid fraction ratio
- Lipid panel:
 - Cholesterol, HDL, triglycerides, LDL cholesterol
- Inflammatory panel:

- CRP, MCP, MMP9, CAM, VCAM, fibrinogen, PAI-1 (antigen), TPA
- B-type natriuretic protein (BNP)
- Panel reactive antibodies (PRA)
- Antibodies: anti-GAD 65, anti-IA2, anti-islet cell, and anti-insulin

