- Fasting capillary glucose level should not exceed 140 mg/dL (7.8 mmol/L) more than three times in the past week (based on measuring capillary glucose levels a minimum of 7 times in a seven day period).
- Fasting plasma glucose level \leq 126 mg/dL (7.0 mmol/L); if the fasting plasma glucose level is $>$ 126 mg/dL (7.0 mmol/L), it must be confirmed in an additional one out of two measurements.
- 2-hour postprandial capillary glucose should not exceed 180 mg/dl (10.0 mmol/L) more than three times in the past week

based on measuring capillary glucose levels a minimum of 21 times in a seven day period.

- Evidence of endogenous insulin production defined as fasting or stimulated C-peptide levels 0.5 ng/mL (0.16 nmol/L)
2. **Hypoglycemic episodes** will be measured by the number and severity of hypoglycemic episodes quantified by the Ryan HYPO Score (31) (see Appendix *HYPO Score sheets*), and the percent reduction will be reported.
 3. **Glucose variability and hypoglycemia duration will be measured by continuous glucose monitoring system (CGMS)** for a 3-day period at three different time points: 1) at screening, 2) one year after first islet transplant, and 3) one year after last islet transplant. The following measurements and analysis will be reported:
 1. Mean glucose concentration
 2. Percent of time in the following ranges:
 - < 60 mg/dl
 - 60-140 mg/dl
 - 141-200 mg/dl
 - > 200 mg/dl

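### The retransplant rule in Protocol 6.5.1 re-applies every exclusion criterion, so read literally item 11 (glucagon-stimulated C-peptide of 0.3 ng/mL or more) makes ineligible a subject whose declining graft still partly works

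*Protocol*

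**What the plan says.** Protocol 6.5.1 has two paragraphs on further infusions.

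- **Second or third infusion.** "Subjects are eligible for further transplant if by the end of the fourth week after the first islet infusion", or after the second, they have not met the insulin-independence criteria. This paragraph carries no condition about exclusion criteria.
- **Retransplantation and/or fourth transplant.** After 30 days or more of insulin independence, subjects qualify if "they present with declining islet function requiring reintroduction of exogenous insulin". The infusion may be given in the first year after the last one or during the 5-year follow-up, "as long as no exclusion criteria are present and avoiding any HLAs" to which donor-specific antibodies may have formed.

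The recipient exclusion list is in Protocol 6.4.2, where any one listed condition excludes. Item 11 reads "C-peptide response to glucagon stimulation (1 mg iv) (any C-peptide ≥ 0.3 ng/mL". Item 21 excludes a previous transplant but makes an exception for islets; item 11 has no such exception.

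The 5-Year Follow-Up text says: "Should the function of the islet graft decline over time and the subject return to insulin therapy, repeat transplant may be considered". Section 6.7 on the 10-year follow-up says the same. SAP 2.5.1 refers back to Protocol 6.5.1 for eligibility for subsequent transplants and adds no exception.

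**The concern.** Item 11 measures residual islet function. At first entry this makes sense, because it selects subjects without meaningful insulin secretion of their own. At retransplant the same measurement reflects the graft. A subject whose graft is declining but not dead can exceed 0.3 ng/mL precisely because the treatment still partly works, so the condition takes back part of what the trigger gives.

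What is at stake is whether such a subject may have another portal infusion. A site that follows the wording withholds it; a site that follows the evident purpose departs from the written rule. The decision also settles which infusion counts as the last one for the analysis at 1 year after the last transplant, which SAP 2.9 and 9.1 add to the protocol's endpoint at 1 year after the first infusion.

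**Working it through.** The plan states no figure on this point, so the check compares the text of the sections and two thresholds.

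**Step 1: which criteria the condition invokes.** The retransplant sentence names no subset. The only recipient exclusion list is 6.4.2, and item 11 is on it. Several items are tied to entry by their own words: 17 and 18 refer to baseline, 34 and 35 to the weeks before enrollment. Item 11 has no such tie.

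**Step 2: whether a subject the rule addresses can meet item 11.** To have been insulin-independent, a subject needed the following (6.10.2): "Evidence of endogenous insulin production defined as fasting or stimulated C-peptide levels 0.5 ng/mL (0.16 nmol/L"; SAP 2.7.2 prints the same limit with a greater-than-or-equal sign. Since 0.5 > 0.3, the protocol's threshold for endogenous production lies above the exclusion limit. A graft that still gives 0.5 ng/mL on the glucagon test therefore meets item 11. So does one that has slipped below 0.5 but remains at 0.3 or above. Only a graft with glucagon-test values under 0.3 is clear of it.

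**Step 3: like subjects compared.** Take illustrative current glucagon-test values in subjects who are on insulin and meet no other exclusion.

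| Current value (ng/mL) | Not independent by week 4 after a first or second infusion | Independent for 30 days or more, then declined |
|---|---|---|
| 0.2 | eligible | eligible |
| 0.4 | eligible | ineligible (item 11) |
| 0.6 | eligible | ineligible (item 11) |

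With the same C-peptide, the subject who never reached independence may be re-infused and the one who reached and lost it may not. Nothing in the protocol gives a reason for the difference.

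**Step 4: whether a disqualifying value would be known.** Section 6.6.7 describes the post-transplant test: "Glucose, C-peptide, and insulin levels are measured before and six minutes after injecting a bolus of 1 mg of glucagon". This is the same 1 mg challenge as in item 11. The row "Glucagon stimulation test" in 6.6.8 is marked after transplant at weeks 6-7, 24 and 52 (3 tests). In 6.6.9 it is marked at months 12, 24, 36, 48 and 60 (5 tests). That gives 3 + 5 = 8 scheduled tests in the period when 6.5.1 allows retransplant, before counting any restart of the visit schedule after a further infusion. A value of 0.3 or more can therefore be on file when the decision is made.

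**Step 5: other criteria that treatment can move.** Item 11 is not the only one. The phase 1/2 adverse-event table at the end of Section 4 reports anemia in 10/10 subjects (compare item 17, hemoglobin), elevated LDL in 2/10 and elevated triglycerides in 2/10 (item 24), and elevated creatinine in 3/10 (item 14, creatinine clearance). Whether these are meant to apply again at retransplant is also unstated.

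**The case against.** The strongest reply is that nobody would read the sentence this way. Sections 4.2 and 6.4 present the list as enrollment criteria. Section 6.6.7 gives infection, malignancy and compliance as examples of what triggers a re-evaluation. The immediate pre-transplant work-up in 6.6.4 includes neither a C-peptide nor a glucagon test. A reading that defeats the sentence's own trigger is unlikely to be the intended one. This stands as evidence of intent: a safety re-check was probably meant. It does not repair the text, because 6.5.1 itself brings the list back at retransplant and nothing elsewhere waives item 11.

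A second reply is that the rule seldom bites, since no glucagon test is required just before retransplant and the follow-up tests are yearly. This limits the point to subjects with a current value of 0.3 or more. A past value alone does not show that the criterion is present now.

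Three stronger readings are tempting, and the documents do not support them.

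- **That the follow-up sections contradict 6.5.1.** They say only that repeat transplant may be considered. That is permissive and can sit alongside the conditions in 6.5.1; silence on C-peptide is not a contrary rule. Section 6.7 also covers years beyond the window that 6.5.1 sets.
- **That re-infusing such a subject would be logged as a protocol deviation.** SAP section 6 ties eligibility deviations to the Inclusion/Exclusion and Study Continuation Record pages of the CRF. Those pages are not in the documents, so this cannot be settled.
- **That a known share of subjects is barred.** Section 4.1.2 describes an earlier series in which most patients still had C-peptide at five years and few were insulin-independent. It gives no C-peptide cut-off, so the number at or above 0.3 ng/mL cannot be derived.

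A fair criticism of the remedy is that exempting item 11 alone could read as confirming that every other item applies. The fix takes this up.

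**Conclusion.** The point holds as a flaw in the wording of an eligibility rule. Read literally, the retransplant condition in 6.5.1 makes ineligible a subject whose current glucagon-stimulated C-peptide is 0.3 ng/mL or more, and so part of the group the paragraph sets out to admit. Subjects whose values have fallen below 0.3 are unaffected, and so is the rule for second and third infusions.

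The size is minor. It bears on individual treatment decisions and, through them, on which infusion is the last. No direction of bias, effect on power or sample size, or number of subjects affected is claimed.

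The conclusion assumes that 6.4.2 is the list that 6.5.1 refers to, and that no waiver of item 11 sits in the Detailed Visit Schedule or Transplant Order appendices, which appear in the available text by title only.

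**What to change.** In the retransplant sentence of Protocol 6.5.1, insert after the mention of exclusion criteria: *other than item 11 (C-peptide response to glucagon)*. Leave the safety exclusions, including item 21, and the avoidance of sensitizing HLAs in force. Item 11 can be separated from them because it measures the function the treatment is meant to restore, not a hazard of giving it.

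In the same edit, have the investigator confirm whether the criteria that immunosuppression affects, items 14 (creatinine clearance), 17 (hemoglobin) and 24 (lipids), are meant to be re-applied at retransplant, and record the answer in the text. If only some criteria apply, a short list of those to be re-checked would be clearest.

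The cost is a few words in one sentence and one decision by the investigator. No tests, visits or patients are added. Exempting item 11 loosens no safety exclusion; items 14, 17 and 24 stay as they are unless the investigator decides otherwise.
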